## 1. AMENDMENT HISTORY

Amendment No.	Protocol Version No.	Date issued	Author(s) of changes	Details of Changes made
1	1.2	22-12-21	[name]	1) Added [name] to the protocol team 2) Added details of stabilisers to blood collection tubes for specific analysis (i.e. incretins, ghrelin and leptin).
2	1.3	26-01-22	[name]	1) Added details on additional faecal analysis
3	1.4	16-03-22	[name]	1) Changed threshold for FEV1:FVC ratio lung function test in screening visit.
4	1.5	26-04-22	[name]	1) Added GP text messages for recruitment.
5	1.6	23-06-22	[name]	1) Increase recruitment capacity from 15 to 20 individuals.
6	1.7	14-07-22	[name]	1) Increase recruitment capacity from 20 to 23 individuals.

## 2. SYNOPSIS

Study Title	The effects of repeated moderate overnight normobaric hypoxia on glucose homeostasis, appetite, body weight, inflammation and oxidative stress in individuals with type 2 diabetes mellitus.
Internal ref. no.	n/a
Problem statement	
The number of people with type 2 diabetes mellitus (T2DM) continuing to rise, this pandemic is expected to reach 700 million people by 2045. T2DM is a metabolic condition characterized by progressive insulin resistance and chronic hyperglycemia (high blood glucose concentrations). Hyperglycaemia increases the risk of both micro- and macrovascular damage, whilst interventions that reduce blood glucose mitigate this risk. Weight loss, achieved through exercise and dietary modification, is effective at reducing hyperglycaemia. However, despite the clear benefits of exercise and weight loss, diverse psychological, sociological and logistical factors can make it difficult for some individuals with T2DM to initiate, or adhere to, these lifestyle interventions. Alternative approaches to treatment are therefore required.
 
The purpose of this research project is to investigate whether 10-days of overnight exposure to moderate hypoxia is effective at improving blood glucose control in individuals with T2DM and to provide insight into the physiological mechanisms responsible for any beneficial effects.

Research question / hypothesis	
Aims:
 
The primary aim of this research project is to investigate whether a 10-days of overnight moderate hypoxia can improve blood glucose control in individuals with T2DM.
 
Objectives:
 
Specifically, our objective is to assess a novel therapeutic intervention for the treatment and management of T2DM which overcomes many of the barriers to uptake and adherence that are associated with some lifestyle interventions such as exercise and weight loss.
 
Hypothesis
 
We hypothesise that 10-days of overnight moderate hypoxia will:
 
 
1. Improve glucose control
 
2. Improve insulin sensitivity
 
3. Reduce appetite / food intake
 
4. Reduce body mass
 
5. Improve inflammatory status
 
6. Improve redox balance
 
7. Increase gut anaerobe content
 
8. Maintain habitual physical activity
 
9. Have no effect on sleep quality
 

Study Design	Single blind, randomized, balanced, crossover design study (i.e. participants will undergo both the hypoxia and sham conditions and will be blinded to the conditions in which they are in).
Study Participants	Individuals with type 2 diabetes
Planned Sample Size	The study of 23 subjects provides adequate power (including a 15% drop-out rate typically seen in our clinical trials): 13 subjects are required to detect a 1 standard deviation change [30] in venous blood [glucose] during a 2 hour oral glucose tolerance test (OGTT (alpha = 0.05; power = 80%)).
Follow-up duration	1 months washout – 10 day intervention
Planned Study Period	1 year
Primary Objective	Post-intervention (sham vs hypoxia) area under curve for venous blood [glucose] during a 2 hour OGTT.
Secondary Objectives	Fasting venous blood [glucose], peak venous blood [glucose] during OGTT, Homeostatic Model Assessment for Insulin Resistance (HOMA-IR), daily glucose excursions (continuous glucose monitoring), and untargeted metabolomics, body mass / composition change, hormonal markers of appetite (e.g. leptin and ghrelin), food intake, gut microbiome, markers of inflammatory status (e.g. interleukin-6; nitrite), redox balance (TNF $\alpha$ ; SOD), HIF-1 $\alpha$ , extracellular HSP70, physical activity and sleep quality.
Primary Endpoint	Post-intervention (sham vs hypoxia) area under curve for venous blood [glucose] during a 2 hour OGTT.
Secondary Endpoints	See secondary objectives.
Intervention (s)	10 days of moderate home-based overnight normobaric hypoxia (F 1 O 2 = ~0.155, or sham hypoxia intervention (F 1 O 2 = 0.2093) using hypoxic ‘pillow tents’.

### 3. ABBREVIATIONS

CHaRT	Clinical, Health and Rehabilitation Team
CRF	Clinical record folder
F I O 2	Fraction of inspired oxygen
HOMA-IR	Homeostatic Model Assessment for Insulin Resistance
NHS	National Health Service
T2DM	Type 2 diabetes mellitus

#### 4. BACKGROUND AND RATIONALE

Type 2 diabetes mellitus (T2DM) is a metabolic condition characterized by progressive insulin resistance and chronic hyperglycemia (high blood glucose concentrations) (10). Hyperglycaemia increases the risk of both micro- and macrovascular damage, whilst interventions that reduce blood glucose mitigate this risk (32). Weight loss, achieved through exercise and dietary modification, is effective at reducing hyperglycaemia (22). However, despite the clear benefits of exercise and weight loss, diverse psychological, sociological and logistical factors can make it difficult for some individuals with T2DM to initiate, or adhere to, these lifestyle interventions (1, 9). With the number of people with T2DM continuing to rise, this pandemic is expected to reach 700 million people by 2045 (24). Thus, there is a clear need for cost-effective interventions that can effectively improve glycaemic control in people with T2DM and which people will adhere to.

A simple exposure to a lowered concentration of inspired oxygen (i.e. hypoxia) may represent such an intervention. In addition to the beneficial effects on glucose homeostasis that have been reported following a single acute hypoxic exposure, repeated intermittent, or continuous, hypoxic exposure may also have therapeutic potential in individuals with T2DM. In rodent models, daily hypoxic exposures returned fasting blood [glucose] to normal levels and increased glucose transporter 4 translocation in mice with T2DM (6, 35). Similar effects on glucose homeostasis have been shown in overweight humans (17) and those with insulin resistance, (during intermittent hypoxic training) which was explained, at least in part, by reduction in body mass (~ 1.2 kg) (27).

Another mechanism for hypoxia induced weight loss could be a shift in the gut microbiome. The gut is a hypoxic environment and as the body becomes systemically hypoxic, anaerobes are likely to become more dominant (11). Some anaerobes are fermenters which not only produce alcohol but also short and medium chain fatty acids which can be metabolised (2, 25). Specifically, the hypoxia-inducible factor (HIF) pathway is attenuated with upregulation of the pyruvate kinase 1 and subsequent inhibition of pyruvate dehydrogenase (21). Moreover, the gene encoding PPAR is selected for during high altitude which leads to a shift in fatty acid

oxidation to glycolytic pathways (19) which in turn will lead to reduction in oxidative phosphorylation and thus oxygen demand, with more efficient oxygen utilisation.

Although hypoxia has received little attention in this kind of clinical context, sleeping in hypoxic environments is already common practice in competitive endurance athletes who attempt to gain an ergogenic benefit through up-regulating erythropoiesis (23). Our own recent work has also demonstrated a significant reduction in body mass in athletes following 10-days of overnight sleeping in a moderate normobaric hypoxic environment ( $F_{I}O_2 = 0.156$ ) combined with moderate daily exercise in a hot environment (23), an effect which did not appear to be due to diuresis. The mechanisms underpinning the improved glycaemic control in response to hypoxia are likely multifactorial. Animal data and *in vitro* human skeletal muscle work (8) suggest that hypoxia may function as an exercise mimetic (i.e the physiological response to exercise without moving) by acting on the same (insulin independent) signalling pathway as that stimulated by muscle contraction, although improved insulin sensitivity in some studies (e.g. (18)) implies that insulin-dependent glucose transport may also have been favourably influenced. Hypoxic stress also activates the hypoxia inducible factor (HIF) pathway, which increases basal metabolic rate, suppresses appetite (20) and promotes a substrate shift towards glucose (15) (i.e. larger anaerobic contribution which is less efficient). HIF activation also induces the heat shock response and increases heat shock protein (HSP) expression which improves insulin resistance and glucose homeostasis in rodents and humans (16). Any reduction in appetite and associated body weight-loss is also likely to be important given that body mass reduction is linked to improved glycaemic control in individuals with T2DM (36).

In summary, T2DM is a condition that affects a significant proportion of the global population, with unsustainable health care implications. This project has the potential to deliver a novel, home based, non-invasive therapeutic intervention for individuals with T2DM. However, there is a dearth of evidence in people with T2DM to show the mechanisms for any beneficial effects. Importantly, the proposed intervention may overcome a number of barriers to uptake and adherence that are associated with these lifestyle interventions, which we anticipate will facilitate higher levels of uptake and compliance. As a consequence, this intervention has the potential to improve outcomes in individuals with T2DM, and to deliver significant financial

savings in terms of the clinical care costs associated with the treatment of type 2 diabetes mellitus.

## 6. AIMS AND OBJECTIVES

### Aims:

The primary aim of this research project is to investigate whether a 10-day overnight moderate hypoxia intervention can improve blood glucose control in individuals with T2DM.

### Hypothesis

We hypothesise that 10-days of overnight moderate hypoxia will:

1. Improve glucose control
2. Improve insulin sensitivity
3. Reduce appetite / food intake
4. Reduce body mass
5. Improve inflammatory status
6. Improve redox balance
7. Increase gut anaerobe content
  
8. Maintain habitual physical activity
9. Have no effect on sleep quality

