### 14.2 Analysis of Endpoints

All data will be tested for normality using the Shapiro-Wilk test. For normally distributed data, paired samples t-tests will be used to assess differences pre and post hypoxic exposures for; blood [glucose] (AUC and peak), insulin sensitivity, eHSP70, IL-6, leptin, ghrelin, TNFa, SOD, HIF-1 $\alpha$  HR, PA and sleep efficiency. For non-parametric data Wilcoxon-Signed rank test will be used for pairwise comparisons. Repeated measures one-way analysis of variance (ANOVA) will be used to identify differences between conditions for SpO2 and [glucose] across time from the CGMs. Mauchly's test of sphericity will be used to determine if any data violated the assumption of spherical data. If violated, sphericity will be accounted for using the Greenhouse-Geisser correction. Where significant differences are observed ( $P < 0.05$ ), post-hoc tests will be performed using LSD pairwise comparisons. Effect sizes will be reported as partial eta squared ( $\eta^2_p$ ) (small = 0.01; medium = 0.06; large = 0.14) [33].

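### Hypotheses 8 and 9 predict no change in physical activity and sleep, but the only analysis assigned to them is a difference test, which cannot support a no-change claim

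*Combined protocol and SAP*

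**What the plan says.** The Synopsis and the Hypothesis list in section 6 give the same nine hypotheses. The first seven predict a change. The last two predict none: "Maintain habitual physical activity" (hypothesis 8) and "Have no effect on sleep quality" (hypothesis 9). Physical activity and sleep quality are secondary outcomes in sections 6.2 and 7.2.

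Section 14.2 states that "paired samples t-tests will be used to assess differences pre and post hypoxic exposures" for a list that runs from blood glucose to "PA and sleep efficiency". The fallback is of the same kind: "For non-parametric data Wilcoxon-Signed rank test will be used for pairwise comparisons". The significance level in that section is 0.05. It is written in the sentence on post-hoc tests, and I take it to apply to the paired tests too.

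The documents give no equivalence or non-inferiority margin, no confidence-interval rule and no power statement for either hypothesis. Section 14.4 says that nothing beyond section 14 is needed by way of an analysis plan. Section 20 mentions effect sizes and confidence intervals as material for designing a later trial.

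**The concern.** A paired difference test takes no change as its null hypothesis. A small P value counts against hypotheses 8 and 9. A large P value says only that the data did not rule out zero, and they may not rule out a sizeable worsening either. The same test suits the endpoints that are expected to change, but it does not match these two.

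If a non-significant result were taken as support, the incentive would run the wrong way: the fewer the completers and the noisier the accelerometer data, the more likely the hypotheses would appear to be borne out. At stake is what the report may say about sleep and daily activity under an overnight intervention, and what is carried into the larger trial foreseen in section 20.

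**Working it through.** **Inputs from the documents**
- Recruitment target: 23 (Synopsis; section 8.2). Section 9 still gives 20.
- Drop-out: 15% (Synopsis; section 9).
- Analysis set: participants who complete all visits (section 14.1).
- Further loss for these endpoints: people with fewer than 4 days of 16 hours' accelerometer wear are excluded (section 10.4).

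**Assumptions**
- Two-sided tests at 0.05; sidedness is not stated.
- Effects and margins in units of the SD of the paired difference, because the documents give no SD for activity or sleep.

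**The plan's own power figure.** The only one concerns glucose: 13 participants for a 1 SD change at alpha 0.05 and 80% power. It does not say which SD is meant. Read as the SD of paired differences, a two-sided paired t-test needs 10 for 80% power; 13 gives 91%. A between-person SD with within-person correlation of 0.3 to 0.4 gives 14 to 12. The figure is therefore not uniquely reproducible. Nothing below depends on it, and it says nothing about activity or sleep.

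**Completers.** 23 × 0.85 = 19.55, so about 19. From section 9, 20 × 0.85 = 17. With no loss, 23.

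**Precision.** The 95% CI half-width is t(0.975, n−1)/√n.
- n = 17: 2.120/4.123 = 0.51 SD
- n = 19: 2.101/4.359 = 0.48 SD
- n = 23: 2.074/4.796 = 0.43 SD

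**Chance of missing a true 0.5 SD change.** The test statistic follows a noncentral t with n−1 degrees of freedom and noncentrality 0.5√n, compared with the critical values above.
- n = 17: noncentrality 2.06, missed 51%
- n = 19: noncentrality 2.18, missed 46%
- n = 23: noncentrality 2.40, missed 37%

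At n = 19 a true 0.3 SD change is missed 76% of the time. The smallest change detectable with 80% power is 0.68 SD.

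**What a test suited to the hypothesis could deliver.** Requiring the 90% CI to lie wholly inside ±margin is the same as two one-sided 5% tests. At n = 19 the 90% half-width is 1.734/4.359 = 0.40 SD. With a 0.5 SD margin, the estimate must therefore fall within about 0.10 SD of zero when the sample SD equals the true one. Exact power when the true difference is zero (margins illustrative):

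| Margin (SD) | n = 17 | n = 19 | n = 23 |
|---|---|---|---|
| 0.4 | 0.07 | 0.10 | 0.19 |
| 0.5 | 0.275 | 0.35 | 0.50 |
| 0.6 | 0.53 | 0.62 | 0.75 |
| 0.7 | 0.74 | 0.80 | 0.89 |

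Eighty per cent power needs a margin of about 0.74, 0.70 and 0.63 SD respectively. At a 0.5 SD margin it needs 36 completers.

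**The case against.** The strongest reply is that the misreading is not in the protocol. A reader might infer that the investigators plan to declare no effect from P>0.05. Section 14.2 names a test and gives no rule for declaring any hypothesis confirmed, so that inference goes beyond the text. This stands. What can be said is that the plan offers no valid way to support hypotheses 8 and 9.

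A reader might also infer that undisturbed sleep is central to the argument that the intervention avoids adherence barriers. The documents do not say so. Sections 2 and 4 describe those barriers as psychological, sociological and logistical, without mentioning sleep, and section 11.2 checks adherence by diary and SpO2. The point should not be given weight on that ground.

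Confidence intervals are foreseen in section 20, and a wide interval would show a reader how little a null result means. This softens the point. But section 20 ties the intervals to planning the next trial, section 14.2 itself names only partial eta squared, and without a margin an interval supplies no criterion for no effect.

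Formal equivalence testing can fairly be called too much for a pilot with no documented margin: with margins of 0.5 to 0.6 SD it would often end as inconclusive even if hypoxia truly did nothing. That stands, and is why the fix offers an estimation route.

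Finally, 19 is derived, not stated. The range 17 to 23 leaves the conclusion unchanged, and wear-time exclusions can only reduce the number.

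**Conclusion.** The point holds as a mismatch between two stated hypotheses and the only analysis assigned to them. With about 19 completers, a non-significant result would be compatible with changes approaching 0.5 SD or more in either direction, and a true 0.5 SD change would go undetected in nearly half of such trials. The sizes rest on assumed completer numbers, two-sided 5% tests and effects in SD units of the paired difference.

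The consequence is limited: both are secondary hypotheses in a self-described pilot, and the primary glucose comparison does not depend on them. Section 14.2's use of pre versus post hypoxia instead of hypoxia versus sham affects every endpoint on its list and adds no weight here, although the fix has to use the sham-controlled contrast. The change should be made, but the trial does not turn on it.

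**What to change.** In section 14.2, for physical activity and sleep efficiency:

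1. Report the hypoxia-minus-sham difference with its confidence interval as the basis for interpretation.
2. State that P>0.05 will not be taken as evidence that activity was maintained or sleep unaffected.
3. Then choose one of two routes:
   - reword hypotheses 8 and 9 as estimation aims; or
   - keep them, name one activity measure and one sleep measure (section 10.4 defines several of each), and have the sponsor justify and fix a margin for each before the data are seen. Claim no effect only if the 90% CI lies inside the margin; otherwise report inconclusive.

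The cost is a short paragraph and no new data or participants. The second route also requires work to justify two margins. The conclusion on sleep and activity may become less favourable: on the second route at n = 19, a truly null effect would be confirmed only about 35% of the time with a 0.5 SD margin, and 80% of the time only with a margin of about 0.7 SD.

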#### 6.1 Primary Objective

Specifically, our objective is to assess a novel therapeutic intervention (hypoxia) on glucose AUC during an OGTT.

#### 6.2 Secondary Objectives

Secondary objectives include fasting venous blood [glucose] peak venous blood [glucose] during OGTT, Homeostatic Model Assessment for Insulin Resistance (HOMA-IR), daily glucose excursions (continuous glucose monitoring), body mass / composition change, gut microbiome, hormonal markers of appetite (e.g. leptin and ghrelin), food intake, markers of inflammatory status (e.g. interleukin-6; nitrite), redox balance (TNF $\alpha$ ; SOD), HIF-1 $\alpha$ , extracellular HSP70, physical activity and sleep quality (accelerometry).

## 7. STUDY DESIGN

### 7.1 Summary of Study Design

Single blind, randomized, balanced, crossover design study (i.e. participants will undergo both the hypoxia and sham conditions and will be blinded to the conditions in which they are in).

### 7.2 Primary and Secondary Endpoints/Outcome Measures

#### *Primary outcome measure*

Post-intervention (sham vs hypoxia) area under curve for venous blood [glucose] during a 2 hour OGTT.

#### *Secondary outcome measures*

Fasting venous blood [glucose] peak venous blood [glucose] during OGTT, Homeostatic Model Assessment for Insulin Resistance (HOMA-IR), daily glucose excursions (continuous glucose monitoring), and untargeted metabolomics, body mass / composition change, hormonal markers of appetite (e.g. leptin and ghrelin), food intake, gut microbiome, markers of inflammatory status (e.g. interleukin-6; nitrite), redox balance (TNF $\alpha$ ; SOD), HIF-1 $\alpha$ , extracellular HSP70, physical activity and sleep quality.

## 8. STUDY PARTICIPANTS

### 8.1 Study Setting

The primary and secondary outcomes will be assessed in the Spinnaker building at the University of Portsmouth. The Clinical Exercise Physiology Laboratory at the University of Portsmouth has a successful history of conducting studies in clinical populations. The laboratory contains state of the art equipment that is required for conducting this study and a research group involving over 20 academics and researchers. Screening bloods will be assessed at Queen Alexandra Hospital, Portsmouth pathology lab or a commercial laboratory. Leptin, ghrelin, interleukin-6, TNFa, SOD, HIF-1 $\alpha$  and extracellular HSP70 concentrations will be quantified using commercially available ELISA assays at UoP (or at UCL with [name]). Profiling of the gut microbiome will be analysed between UoP (in [name] Laboratory) and the University of Southampton. Nitrite will be analysed at Loughborough University using a Sievers nitric oxide analyser (Sievers NOA 280i, Analytix Ltd, Durham, UK) with our established technique (5, 28-31). Metabolomics will be analysed at the University of Liverpool (in [name] laboratory).

### 8.2 Overall Description of Study Participants

We will recruit 23 participants with T2DM as defined by the World Health Organization to take part in our simulated altitude exposure study (i.e. normobaric decreased FiO2).

### 8.3 Eligibility Criteria

Note: Altitudes < 2,500m (~0.15 FIO2) are similar to those in a commercial aircraft and are considered safe for individuals with stable coronary artery disease (Bonadie et al., 2016).

#### **Inclusion Criteria**

- 1) Males and females with T2DM (as diagnosed with the WHO criteria).
- 2) Ability to understand the study and provide informed consent.

#### **Exclusion Criteria**

Individuals with contraindications to hypoxic exposure such as;

- 1) obstructive sleep apnoea,
- 2) extant cardiac conditions
- 3) on medications such as SGLT2 inhibitors or PPAR antagonists
- 4) glycated haemoglobin < 48
- 5) sickle anemia,
- 6) thalassemia,
- 7) haemoglobinopathy
- 8) FVC < 80% of predicted FVC
- 9) FEV1:FVC ratio < 5th percentile for age and sex (as according to the European Respiratory Society and American Thoracic Society guidelines) (37) .

,

## 9. SAMPLING

The study of 20 subjects provides adequate power (including a 15% drop-out rate typically seen in our clinical trials): 13 subjects are required to detect a 1 standard deviation change [30] in venous blood [glucose] during a 3 hour oral glucose tolerance test (OGTT (alpha = 0.05; power = 80%)). Seasonal changes will be recorded and corrected for as a covariate.

